9.9 Planned interim analysis and data monitoring

No interim analysis or data monitoring are planned in this study.

9.10 Determination of sample size

Based on the study PK and PD objectives, the total planned number of healthy study participants will be 44, including 22 evaluable participants for Part A and 22 evaluable participants for Part B.

For Part A, the sample size is based on pragmatic considerations and the ability to detect an ethanol effect on PD assessments (CNS variable). A sample size of 22 evaluable study participants provides 80% power to detect an ethanol effect in a difference in means of 3.96 (% points) for the smooth pursuit test, which is the most sensitive CNS variable to ethanol effects, assuming a SD of difference of 6.0 (% points) based on previous ethanol clamp interaction studies and using a paired t-test 2-sided with a 0.05 significance level. This sample size is also valid for the CBD effect assessment (Part B).

For Part B, a sample size of 22 evaluable study participants is needed to assess the PK interaction between PSL and CBD, and to estimate the mean PSL AUC_{τ} ratio of with/without CBD of 1.5 with a half-width of the CI of 0.3. This sample size has been evaluated with a conditional probability of 90%, assuming an inter-participant coefficient of variation of 45% of PSL AUC_{τ} (observed in study UP0057), correlation of 0.5, 2-sided and $\alpha = 0.05$. A sufficient number of healthy study participants (up to 20) will be selected to have 16 completed study participants.

Regarding the assessment of the single dose formulation of CBD (under fasted conditions) in Part B (study formulation vs Epidiolex formulation from literature data), 16 healthy study participants are required to assess the similarity of the 2 formulations (equivalence range of 50 to 200% based on the high variability of CBD) with a 80% power and assuming an expected geometric mean ratio of AUC and C_{max} between 0.8 and 1.3, and inter-participant CV of 80% (based on CBD literature) and correlation of 0.5.

Sample size computations were performed using SAS version 9.4 (Proc Power).

Drop outs will be replaced at the discretion of the Investigator and Sponsor.

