2.3 Determination of sample size

Based on the study PK and PD objectives, the total planned number of healthy study participants will be 44, including 22 evaluable participants for Part A and 22 evaluable participants for Part B.

For Part A, the sample size is based on pragmatic considerations and the ability to detect an ethanol effect on PD assessments (CNS variable). A sample size of 22 evaluable study participants provides 80% power to detect an ethanol effect in a difference in means of 3.96 (% points) for the smooth pursuit test, which is the most sensitive CNS variable to ethanol effects, assuming a SD of difference of 6.0 (% points) based on previous ethanol clamp interaction studies and using a paired t-test 2-sided with a 0.05 significance level. This sample size is also valid for the CBD effect assessment (Part B). The sample size calculation performed does not assess the difference in means between PSL+Ethanol effect vs PSL+Placebo, as the expected difference between the interaction is unknown but similarly a difference of 3.96 (% points) could be detected.

For Part B, a sample size of 22 evaluable study participants is needed to assess the PK interaction between PSL and CBD, and to estimate the mean PSL AUC_{τ} ratio of with/without CBD of 1.5 with a half-width of the CI of 0.3. This sample size has been evaluated with a conditional probability of 90%, assuming an inter-participant coefficient of variation of 45% of PSL AUC_{τ} (observed in study UP0057), correlation of 0.5, 2-sided and $\alpha = 0.05$. A sufficient number of healthy study participants (up to 20) will be selected to have 16 completed study participants.

Regarding the assessment of the single dose formulation of CBD (under fasted conditions) in Part B (study formulation vs Epidiolex formulation from literature data), 16 healthy study participants are required to assess the similarity of the 2 formulations (equivalence range of 50 to 200% based on the high variability of CBD) with a 80% power and assuming an expected geometric mean ratio of AUC and C_{max} between 0.8 and 1.3, and inter-participant CV of 80% (based on CBD literature) and correlation of 0.5.

Sample size computations were performed using SAS version 9.4 (Proc Power).

Drop outs will be replaced at the discretion of the Investigator and Sponsor.

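### Part A sample size: 22 participants, 80% power and a 3.96-point difference do not fit together; on the stated inputs 3.96 is the 80% figure for 20 participants

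*Protocol*

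**What the plan says.** The Part A calculation is in Protocol section 9.10 and is repeated in SAP section 2.3. All of its inputs are printed:

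- **Size, power and difference:** "A sample size of 22 evaluable study participants provides 80% power to detect an ethanol effect in a difference in means of 3.96" percentage points on smooth pursuit, the Part A primary endpoint.
- **Variability:** "assuming a SD of difference of 6.0 (% points) based on previous ethanol clamp interaction studies".
- **Test:** "using a paired t-test 2-sided with a 0.05 significance level", computed in SAS 9.4 Proc Power.
- **Dropouts:** the 22 are described as evaluable. No inflation rate is given for Part A, and "Drop outs will be replaced at the discretion of the Investigator and Sponsor".

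The section also describes the Part A size as partly pragmatic, and says the same size serves the assessment of the CBD effect in Part B.

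SAP section 2.3 makes one addition. It says the calculation was not made for PSL+Ethanol versus PSL+Placebo because the size of that difference is unknown, and then says that "similarly a difference of 3.96 (% points) could be detected". SAP section 10.1.2.1 names that contrast as the primary comparison.

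**The concern.** Sample size, power, detectable difference, SD and test are all given, so any one of size, power and difference is fixed by the others. Here they disagree. A difference quoted to two decimals next to 80% power reads as a solved detectable difference for 22 participants, and it is not that value.

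This is the only power statement for the Part A primary endpoint. SAP section 2.3 then carries 3.96 to the primary contrast, and Protocol section 9.10 relies on the same size for the CBD effect in Part B. Anyone who reruns the calculation from the printed inputs will fail to reproduce it, and a report that copies the sentence would misdescribe the sensitivity of the design.

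**Working it through.** **Inputs** (Protocol section 9.10, repeated in SAP section 2.3): difference d = 3.96 points; SD of the paired difference s = 6.0 points; two-sided α = 0.05; n = 22; stated power 80%.

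**Formula.** Exact power of a paired t-test comes from the noncentral t distribution with n − 1 degrees of freedom and noncentrality

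λ = (d / s) × √n

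Power = P(T > t_crit) + P(T < −t_crit), where t_crit is the 0.975 quantile of the central t with n − 1 degrees of freedom. The detectable difference is the d at which this power equals 0.80.

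**Step 1: the plan's own figure, n = 22.**

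λ = (3.96 / 6.0) × √22 = 0.66 × 4.690 = 3.096, with 21 degrees of freedom.

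Power = **83.9%**, against 80% stated. Solving for 80% power gives a detectable difference of **3.76** points, against 3.96 stated. The stated figure is not reproduced.

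**Step 2: which n does return 80% and 3.96?**

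| n | Power for 3.96 points | Difference detectable with 80% power |
|---|---|---|
| 19 | 77.7% | 4.08 |
| 20 | 79.95% | 3.963 |
| 21 | 82.0% | 3.86 |
| 22 | 83.9% | 3.76 |

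At n = 20, λ = 0.66 × 4.472 = 2.952 with 19 degrees of freedom. Power is 79.95%, and the detectable difference of 3.963 rounds to 3.96. Under the named test, only n = 20 matches the stated pair at the printed precision.

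**Step 3: can another reading rescue n = 22?** Power for 3.96 points with 22 participants:

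| Variant | Power |
|---|---|
| 20 degrees of freedom (two sequences) | 83.7% |
| 18 degrees of freedom (four sequences) | 83.3% |
| SD 5.95 (rounds to 6.0) | 84.5% |
| SD 6.05 (rounds to 6.0) | 83.3% |
| Normal approximation | 87.2% |
| One-sided 0.05 | 91.1% |

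The closest of these is 3.3 points above 80%. Rounding of the power does not help either: for power between 79.5% and 80.5%, the detectable difference at n = 22 runs from 3.74 to 3.78. For 22 participants to give exactly 80% at 3.96, the SD would have to be about 6.32, which does not round to 6.0.

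**Step 4: size of the error.**

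- Power: 83.9% − 80% = 3.9 percentage points understated.
- Detectable difference: 3.96 − 3.76 = 0.20 points overstated; 0.20 / 3.96 = 5.1%.

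**The case against.** Four points can be made for the plan.

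1. **80% may mean at least 80%.** On that reading the sentence is literally true, since 83.9% exceeds 80%. The SAP addition is also true as written, because a study able to detect 3.76 points can detect 3.96. Neither document calls 3.96 the minimum detectable difference. This stands as a reading of the words, but it does not make 80% the power, or 3.96 the 80% detectable difference, for 22 participants.

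2. **The number may be 20 plus an allowance.** An inflation of roughly 9 to 10% (an assumption) would take 20 to about 22. The text does not support this: the 22 are called evaluable, dropouts are handled by replacement, and the only mention of 20 in that section concerns Part B. The origin at n = 20 is itself an inference, since a normal approximation at n = 18 also gives 3.96. That approximation is not the test the plan names, and the mismatch at n = 22 does not depend on where 3.96 came from.

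3. **The sample size is unaffected.** The smallest n with at least 80% power for 3.96 points is 21 (82.0%), and the plan says its choice was partly pragmatic. This stands in full: Part A is not underpowered on its own assumptions.

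4. **The practical effect is small.** No decision rule uses 3.96, and the PD contrasts are reported as estimates with 95% confidence intervals, so the achieved precision will come from the data. The SAP also admits that the calculation was not made for the primary contrast. This stands too, and it is why the point is minor.

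**Conclusion.** The concern holds. With an SD of difference of 6.0 and a two-sided 0.05 paired t-test, 22 evaluable participants give 83.9% power for 3.96 points, or 80% power for 3.76 points. The printed combination is not the result for 22; it matches 20.

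The error is in the safe direction, and it casts no doubt on the adequacy of 22 or on the validity of Part A. It is a wrong operating characteristic for the primary endpoint, to be corrected as an editorial matter.

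The conclusion takes the plan's SD and test as given. For the primary contrast it also assumes, as the SAP implicitly does, that the SD of 6.0 applies to PSL+Ethanol versus PSL+Placebo as it does to the ethanol effect alone.

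**What to change.** Change one sentence in Protocol section 9.10 and the matching sentence in SAP section 2.3. Keep the SD of 6.0 and the two-sided 0.05 paired t-test, and state one of the following:

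- 22 evaluable participants give about 84% power to detect 3.96 points; or
- 22 evaluable participants give 80% power to detect 3.76 points.

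If 20 was the computed number and 22 contains an allowance, say so: give 3.96 as the figure for 20 completers and state the allowance.

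In SAP section 2.3, carry the corrected figure into the remark on PSL+Ethanol versus PSL+Placebo, and state that it assumes the same SD of difference for that contrast.

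The cost is one sentence in each document. Design, enrolment and analysis do not change.

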9.5.3 Cannabidiol interaction on PSL (Part B)

Effects of CBD on log-transformed PK parameters ($C_{\max,ss}$, AUC_{τ}) of PSL and its metabolites will be analysed with a mixed model of variance for a 2x2 cross-over with fixed factors of treatment, sequence, period and random factor study participant within sequence. Estimation of geometric ratio of PK parameters between the 2 treatments (CBD+PSL vs PSL) with their 90% CI will be provided. The PK of PSL without CBD is obtained in Part B Treatment Period 2.

9.5.4 PSL interaction on CBD (Part B):

Effects of PSL on log-transformed PK parameters ($C_{\max,ss}$, AUC_{τ}) of CBD and its metabolites will be analysed with a mixed model of variance for a 2x2 cross-over with fixed factors of treatment, sequence, period and random factor study participant within sequence. Estimation of geometric ratio of PK parameters between the 2 treatments (PSL+CBD vs PSL placebo+CBD) with their 90% CI will be provided.

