9.1.2.3 CBD interaction on PSL (Part B)

The log-transformed PK parameters ($C_{\max,ss}$, AUC_{τ}) of PSL and its metabolites, and the metabolite to parent ratio based on AUC_{τ} (no transformation required) will be analyzed

separately by a mixed ANOVA with treatment (PSL (Treatment Period 2) and CBD+PSL (Treatment Period 4/5)) as a fixed effect and study participant as the random effect to assess the effects of CBD on PSL. The SAS code stated in [Section 9.1.2](#) will be used with period removed.

Point estimates for the ratio of geometric means with and without CBD (CBD+PSL vs PSL) and the respective 2-sided 90% CIs will be computed using the least squares means and the root mean squares of error from the mixed effects model, based on the log-transformed data with subsequent exponential transformation.

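### The Part B precision statement is written for a 95% CI, but the planned CI is 90%; at 95% the claimed 90% probability does not follow for n=22 under the main readings

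*Protocol*

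**What the plan says.** Protocol 9.10 says: "For Part B, a sample size of 22 evaluable study participants is needed to assess the PK interaction between PSL and CBD". The target is a mean PSL AUCτ "ratio of with/without CBD of 1.5 with a half-width of the CI of 0.3". The inputs are given as "assuming an inter-participant coefficient of variation of 45% of PSL" AUCτ and "correlation of 0.5, 2-sided and $\alpha = 0.05". SAP 2.3 repeats the paragraph, including "This sample size has been evaluated with a conditional probability of 90" per cent. Protocol 9.10 adds: "Sample size computations were performed using SAS version 9.4 (Proc Power").

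Neither section states the confidence level in words. Neither says whether the 0.3 is on the ratio scale or the log scale, or which SD was entered.

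On the analysis side, protocol 9.5.3 takes log-transformed Cmax,ss and AUCτ and says: "Estimation of geometric ratio of PK parameters between the 2 treatments (CBD+PSL vs PSL) with their 90% CI will be provided". SAP 9.1.2.3 agrees: "the respective 2-sided 90% CIs will be computed using the least squares means", followed by exponentiation.

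**The concern.** Two-sided alpha 0.05 corresponds to a 95% CI. The same section uses two-sided 0.05 in that ordinary sense for the Part A t-test, so the reader has no cue to interpret it differently for Part B. The stated precision therefore refers to an interval that the primary analysis will not report.

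PSL AUCτ is a Part B primary endpoint, and this paragraph is the only precision justification given for it. Taken literally, it promises a 95% CI of about 1.2 to 1.8 around 1.5 nine times in ten. If the design does not deliver that, the stated basis for 22 is wrong as written, even if 22 suits the interval actually planned.

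**Working it through.** **Inputs (protocol 9.10, SAP 2.3).** n = 22; ratio 1.5; half-width 0.3; CV 45%; correlation r = 0.5; probability 0.90.

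**Assumptions.** The comparison is treated as paired with n − 1 = 21 df, which matches the SAP 9.1.2.3 model (treatment fixed, participant random) with complete data. Conditional probability is read as conditional on the CI covering the true value.

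**SD of the paired difference.** σd = σ·√(2(1 − r)), so at r = 0.5, σd = σ.
- Log scale: σ = √ln(1 + 0.45²) = 0.4294.
- Ratio scale, CV applied to the ratio of 1.5: σ = 1.5 × 0.45 = 0.675.
- Raw scale, CV applied to a mean of 1: σ = 0.45.

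**Formula.** The half-width is t·s/√n. It is at most h when s ≤ s_max = h·√n/t. The unconditional probability is P(χ²₂₁ ≤ 21·s_max²/σd²). The conditional version also requires coverage and is found by integration.

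**Reproducing the plan's 22 (ratio scale, 90% CI).** t = 1.7207 and s_max = 0.3 × 4.6904/1.7207 = 0.8177. Then 21 × (0.8177/0.675)² = 30.82. The unconditional probability is 0.923 and the conditional one 0.917. At n = 21 the conditional value is 0.879, so 22 is the smallest n that reaches 0.90.

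**Same calculation at the stated alpha (95% CI).** t = 2.0796 and s_max = 0.6766. Then 21 × (0.6766/0.675)² = 21.10. The unconditional probability is 0.547 and the conditional one 0.534. The n needed is 29.

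**Planned log analysis, back-transformed.** Half the total width is (U − L)/2. It scales with the estimated ratio, so the estimate and s were both simulated.

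| CI | n | P((U − L)/2 ≤ 0.3), unconditional / conditional |
|---|---|---|
| 95% | 22 | 0.633 / 0.629 |
| 95% | 28 | 0.893 / 0.894 |
| 95% | 29 | 0.918 / 0.919 |
| 90% | 20 | 0.862 / 0.863 |
| 90% | 21 | 0.898 / 0.900 |
| 90% | 22 | 0.926 / 0.929 |

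Fixing the estimate at 1.5 instead gives slightly higher conditional values at n = 22: 0.637 for the 95% CI and 0.954 for the 90% CI.

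**Other readings at 95%, with 90% conditional probability.**

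| Reading | n needed | Probability at n = 22 |
|---|---|---|
| 0.3 directly on the log scale (SD 0.4294) | 15 | above 0.99 |
| Raw scale, SD 0.45 | 16 | above 0.99 |
| Log model, lower arm only, ln(1.5/1.2) | 23 | 0.877 |
| Log model, upper arm only, ln(1.8/1.5) | 32 | 0.417 |
| Raw paired difference, SDs 0.45 and 0.675 | 24 | 0.827 |
| Average of those two SDs, 0.5625 | 22 | 0.912 |

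**Typical intervals at n = 22, log analysis (σd entered for s).** The standard error is 0.4294/√22 = 0.0916.
- 90% CI: 1.7207 × 0.0916 = 0.1575, so 1.5·e^(±0.1575) = 1.28 to 1.76.
- 95% CI: 2.0796 × 0.0916 = 0.1904, so 1.5·e^(±0.1904) = 1.24 to 1.81.

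**The case against.** The strongest reply is that 22 can be reproduced. The documents never write out a 95% CI, and the scale is open. With the 90% CI of protocol 9.5.3 and SAP 9.1.2.3 and a ratio-scale SD of 0.675, 22 is exactly the smallest adequate number. One 95% reading, the averaged SD of 0.5625, also lands on 22, and two others come within two participants (23 and 24). No acceptance range is set for the Part B comparison, so no decision rule depends on this half-width. Estimand, analysis and enrolment are unaffected.

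Most of that stands. A reader might infer that 22 cannot be obtained on any scale; the documents do not support this, because they leave scale and SD unstated and a simple reading does give 22. A reader might also infer that Part B is too small; that does not follow either, because the planned 90% CI meets the 0.3 target at 22.

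The reply does not rescue the text as written. Its simplest match replaces the stated two-sided 0.05 with 0.10. The 95% match needs an averaged SD that appears nowhere in the documents, and the near misses at 23 and 24 fall short of 90% at n = 22.

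**Conclusion.** The point holds as a mismatch of confidence level together with an unstated scale and SD. At the stated alpha, the planned log analysis delivers a half-width of 0.3 or less about 63% of the time at n = 22, against the stated 90%; about 29 participants would be needed. The ratio scale with SD 0.675 gives about 53%, and again 29. Setting 0.3 against an SD of 0.43 to 0.45 gives 15 to 16. At the 90% level actually planned, n = 22 gives about 93% (log analysis) or 92% (ratio scale), so the design is adequate for its own analysis.

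That alpha 0.05 per side was labelled two-sided is the likeliest explanation, but it is an inference that the documents do not confirm. The figures rest on the stated CV and correlation, a paired analysis with 21 df and, for the log-analysis figures, half the back-transformed total width as the half-width.

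**What to change.** In protocol 9.10 and SAP 2.3, for the Part B PK paragraph:

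- Replace the two-sided alpha 0.05 with a two-sided 90% CI (alpha 0.10).
- State the scale of the half-width and the SD used.
- Restate the precision: 22 evaluable participants give an expected 90% CI of about 1.28 to 1.76 around a ratio of 1.5, with half the back-transformed width at or below 0.3 with about 93% probability (log analysis, SD 0.4294, estimate allowed to vary).
- If a 95% CI is really intended, give its probability at n = 22 (about 63%) in place of 90%.

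The sponsor should check the original sample-size run to confirm which level and SD were entered. The cost is wording in two documents; the number of participants and the planned 90% CI analysis do not change.

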4.1.2 Part B

Treatment Period 1 of Part B will be conducted in a sentinel cohort of healthy study participants in order to evaluate CBD safety and PK exposure under a single dose of CBD 10mg/kg (fasted conditions). The results of the PK analysis will be compared to published PK data of CBD (dose of 750mg in fasted conditions) obtained in similar conditions with Epidiolex® (Taylor et al, 2018). The decision to continue on with the rest of Part B or terminate the study following the first CBD dose in Treatment Period 1 of Part B will be made pending the outcome of the analysis of CBD safety and exposure. A difference between the PK results in the present study and the literature findings requiring a >2-fold dose adjustment will be considered as not manageable and would result in termination of the study. If a dose adjustment \leq 2-fold is needed, then the study will proceed with the second dose of CBD of Treatment Period 1 in Part B. If the observed CBD exposure matches the data from the literature, then study will proceed directly to Treatment Period 2 of Part B (no second dosing of CBD will be required). Treatment Period 2 cannot commence until the results from Treatment Period 1 are analyzed.

A washout of at least 6 days will occur between Treatment Period 1 and Treatment Period 2. Treatment Period 2 will include 7 days of treatment with open-label PSL treatment. Treatment Period 3 starts after a washout of minimally 6 days for all study participants, and includes an ambulatory open-label CBD up titration of 16 days toward a maintenance level of 10mg/kg BID.

Treatment Periods 4 and 5 are 2-way cross-over, double-blind and placebo-controlled periods with PSL up titrated to a maintenance level of 200mg BID through Day 5 and subsequent down titration until Day 8. A maintenance dose of 10mg/kg BID CBD will occur in-house between Treatment Periods 4 and 5. Cannabidiol down titration starts in Treatment Period 6.

Study participants will be discharged at the end of Treatment Period 6 and return for a SFU Visit 7 to 10 days after the final dose of CBD. See Section 1.3.2 for the schedule of activities for Part B.

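### The 80% power for the Part B cannabidiol formulation check assumes paired data, but the comparator is published data from other people

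*Protocol*

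**What the plan says.** Protocol 9.10, repeated in SAP 2.3, describes the comparison as "study formulation vs Epidiolex formulation from literature data" and states that "16 healthy study participants are required to assess the similarity of the 2 formulations". The margin is an "equivalence range of 50 to 200% based on the high variability of CBD". Power is 80%, "assuming an expected geometric mean ratio of AUC and C_{max} between 0.8 and 1.3", with "inter-participant CV of 80% (based on CBD literature) and correlation of 0.5". The computations are attributed to SAS Proc Power. No significance level is given for this calculation, and no number of published participants.

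Protocol 4.1.2 confirms the comparator: the Treatment Period 1 results "will be compared to published PK data of CBD (dose of 750mg in fasted conditions") obtained with Epidiolex. SAP 4.3 says the same. The optional second dose in Treatment Period 1 is again the study's own CBD, and SAP 4.3 again compares it with the published data.

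**The concern.** A correlation between test and reference reduces the variance of their difference only when each participant contributes both measurements. Here the test values come from 16 trial participants and the reference is a summary of other people in a published study. There are no pairs, so the correlation is zero. The published mean also has its own sampling error, which the calculation must either include or explicitly set to zero.

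This matters because 9.10 offers no other justification for the 16, and because the comparison gates the rest of Part B. Treatment Period 2 cannot start until it has been assessed, and a discrepancy calling for more than a 2-fold dose adjustment leads to termination. A team that relies on the stated power would think the exposure ratio better determined than it will be.

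**Working it through.** **Inputs from Protocol 9.10:** n = 16; limits 0.5 and 2.0 (log scale ±0.693); true geometric mean ratio (GMR) 0.8 to 1.3; inter-participant CV 80%; correlation 0.5.

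**Assumed:** two one-sided tests at 0.05 each (a 90% confidence interval). The text states no alpha; this choice reproduces the stated figure. The number of published participants, m, is not in the documents and is varied.

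**Harder end of the GMR range.** The distance to the nearer limit is ln(2/1.3) = 0.431 at GMR 1.3 and ln(0.8/0.5) = 0.470 at GMR 0.8, so 1.3 governs.

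**Log-scale SD.** √ln(1 + 0.8²) = √0.4947 = 0.7033.

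**Step 1: reproduce the plan (paired).**
- Correlation 0.5 on the original scale becomes ln(1 + 0.5 × 0.8²)/ln(1 + 0.8²) = 0.561 on the log scale.
- SD of the paired log difference = √(2 × 0.4947 × (1 − 0.561)) = 0.659.
- SE = 0.659/√16 = 0.165, with 15 df.
- Exact power at GMR 1.3 is 77.7% for n = 15 and 80.2% for n = 16. At GMR 0.8 with n = 16 it is 85.9%.

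Sixteen is therefore the smallest n reaching 80% at GMR 1.3, which matches the stated figure.

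**Step 2: no pairing, published mean treated as an error-free constant.**
- SE = 0.7033/√16 = 0.1758, with 15 df.
- Power is 75.5% at GMR 1.3, 96.5% at 1.0 and 81.7% at 0.8. Reaching 80% at GMR 1.3 takes 18 participants.

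**Step 3: no pairing, published mean from m independent people with the same CV.** SE = 0.7033 × √(1/16 + 1/m), with 14 + m df.

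| m (assumed) | GMR 1.3 | GMR 1.0 | GMR 0.8 |
|---|---|---|---|
| 6 | 21% | 28% | 23% |
| 12 | 43% | 61% | 48% |
| 16 | 50% | 72% | 55% |
| 30 | 62% | 86% | 68% |
| 60 | 69% | 93% | 76% |
| 100 | 73% | 95% | 79% |
| 1000 | 78% | 98% | 84% |

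At m = 1000 power slightly exceeds the Step 2 value because the pooled variance has more degrees of freedom. The limit for GMR 1.3, with an error-free reference and a known variance, is Φ(0.431/0.1758 − 1.645) = Φ(0.805) = 79%, still under 80%. At GMR 0.8, 80% needs an error-free reference or m of about 114 or more.

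**Step 4: precision.** With a fixed reference, the 90% interval is the estimate times or divided by exp(1.753 × 0.1758) = 1.36. Adding literature error gives a factor of 1.44 at m = 30 and 1.53 at m = 16.

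**The case against.** - **The gate is not an equivalence test.** Protocol 4.1.2 and SAP 4.3 define it by the size of the dose adjustment needed, the sponsor's study team decides, and SAP 4.7 marks equivalence as not applicable. If the rule is read as a point-estimate rule (an assumption), the chance that the observed ratio lies within 0.5 to 2.0 at a true GMR of 1.3 is 99% with a fixed reference, and 90% to 98% for m = 6 to 30. A discrepancy within 2-fold leads to a second dose, not to termination. This stands: the powers above are not the chances of passing the gate, which limits the consequence. It does not make the stated power correct.
- **The loss may be small.** With a fixed reference, power falls below 80% only near the 1.3 edge (81.7% at 1.25, 75.5% at 1.3), and every much lower figure depends on an m that the documents do not give. This also stands, but the plan nowhere says the reference is taken as fixed, and it claims 80% across the whole range up to 1.3.
- **The reproduction depends on unstated choices.** With alpha 0.025 per side, paired power at GMR 1.3 is 68.6%. With correlation 0.5 applied on the log scale it is 75.5%, identical to a fixed reference because the SD of the difference then equals 0.7033. So 0.5 could have been a way of coding a fixed reference. In that case 16 does not give 80% at GMR 1.3, and the stated figure is still not met.

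**Conclusion.** The concern holds. The stated 16 participants and 80% power correspond to a paired design that the trial does not have. Without pairing, 80% is not reached at a GMR of 1.3 under any reading: 75.5% with an error-free published mean, 21% to 73% for 6 to 100 published participants, and 79% in the limit. At GMR 0.8 the claim survives only with an error-free reference (81.7%) or a very large published sample.

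These figures assume CV 80%, one-sided tests at 0.05 each, lognormal data and, in Step 3, the same CV in the published sample. The shortfall that can be computed without assuming m is about 5 percentage points at GMR 1.3 (80.2% to 75.5%). This is an unsupported sample-size justification for a go/no-go exposure check. It does not affect a confirmatory analysis or the 22 participants planned for the Part B interaction analyses, and it should be corrected.

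**What to change.** In Protocol 9.10 and SAP 2.3, keep 16 participants and remove the correlation. State the alpha, and whether the published mean is treated as fixed or as having sampling error. Then do one of the following:

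- **Restate the power.** With a fixed reference, about 75% at GMR 1.3 and 82% at GMR 0.8. Otherwise give the two-sample value using the number of participants in the published study.
- **Restate 16 as a precision.** The 90% confidence interval for the geometric mean ratio is about the estimate times or divided by 1.36, before literature error.

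In either case, add to SAP 4.3 that the ratio and its 90% confidence interval are reported when the Treatment Period 1 decision is made. The go/no-go rule itself is unchanged. The cost is wording and a less favourable stated figure; no additional participants are needed.
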